Protocol Title: Multi-national, multi-center randomized controlled trial to evaluate the clinical utility of non-invasive endometrial receptivity test ora™ in patients with implantation failure

Sponsor: Inti Inc., Taiwan

Intended use: The ora™ test is a laboratory-developed test (LDT) designed to analyze the expression profile of miRNA isolated from plasma. It is intended to identify the optimal window of implantation (WOI) in patients undergoing in vitro fertilization (IVF).

Investigational product/ Model name : Non-invasive endometrial receptivity test / ora™

Objective: To evaluate the clinical utility of non-invasive endometrial receptivity test (ora™) in patients with implantation failure.

Population: Patients who have experienced at least one implantation failure with a euploid or low-level mosaic (< 30%) embryo transfer in the past two years.

Sample Size: The study is expected to enroll up to 800 subjects.

Study design:

- Study type: Prospective
- Blinding : No
- Randomization: Yes
- Study location: Multi-national and multi-center
- Study Period: 6-15 months
- This study aims to enroll subjects who have experienced at least one implantation failure with a euploid or low-level mosaic (< 30%) embryo transfer in the past two years. Subjects should have a euploid embryo, and will be randomly assigned into two groups: control and study group. The study group will undergo frozen embryo transfer based on ora™ timing, while the other group will adhere to the standard timing protocol. The subjects will provide blood samples for the ora™ test during the mock cycle for the study group or during the frozen embryo transfer cycle for the control group. The study will compare pregnancy outcomes to assess whether ora™ timing provides clinical benefits to the patients.

Endpoints (Outcome measure) :

Primary endpoint:

Clinical pregnancy, defined as presence of one or more intrauterine gestational sacs after 6 weeks of gestation.

Secondary endpoint

1. Ongoing pregnancy, defined as presence of fetal heartbeat after 12 weeks of gestation.
2. Live birth, defined as baby survival after 20 weeks of gestation.
3. Abortion and miscarriage rates.
4. Frequency and intensity of adverse events (AEs).

CLINICAL STUDY PROTOCOL

Title: Multi-national, multi-center randomized controlled trial to evaluate the clinical utility of non-invasive endometrial receptivity test (ora™) in patients with implantation failure

Doc. No.	ORA-PTL-2024-01
Version	1.0
Date	2024/01/10

Inclusion/Exclusion Criteria :

Inclusion Criteria:

1. Patients who have at least one implantation failure with a euploid or low-level mosaic (< 30%) embryo transfer in the past two years.
2. Females within 28-45 years old.
3. Those who agree to undergo one mock cycle for ora™ test and execute single frozen embryo transfer in the later cycle.
4. Those who has at least one remaining euploid or low-level mosaic (< 30%) embryo.

Exclusion Criteria:

1. Known uterine factor (such as endometriosis, uterine fibroids) impacting the endometrium.
2. Presence of any clinically relevant systemic disease (such as immune disease) that contraindicates assisted reproductive technology.
3. Body mass index (BMI) exceeds than 30 kg/m².

Statistical Methodology:

1. The outcome of clinical pregnancy, ongoing pregnancy and live birth rate per transfer will be compared between the study and control groups by chi-square analysis.
2. The quantitative outcomes such as gestational age and BMI, etc. will be compared between treatment groups by the Mann-Whitney U test.

CLINICAL STUDY PROTOCOL

Title: Multi-national, multi-center randomized controlled trial to evaluate the clinical utility of non-invasive endometrial receptivity test (ora™) in patients with implantation failure

Doc. No.	ORA-PTL-2024-01
Version	1.0
Date	2024/01/10

2. Introduction

2.1. Background and Study Rational

The successful implantation of blastocysts is a crucial milestone in human reproduction, requiring a harmonious alignment between a viable embryo and a receptive endometrium. Next-generation Sequencing (NGS) technology allows us to explore the intricate transcriptomic details of the human endometrium throughout the menstrual cycle.¹ By analyzing the gene expression patterns in the human endometrium, we can identify distinctive gene expression patterns, particularly during the receptive phase.²

Endometrial receptivity testing has emerged as an evaluation tool that takes advantages of the unique gene expression signature of the endometrium during the implantation window.³ One innovative test is the ora™, which uses blood samples to examine over 110 differentially expressed miRNAs.⁴ The ora™ test categorizes the receptivity stages into three phases: pre-receptive, receptive, and post-receptive. Based on the results, patients receive recommendations for the timing of frozen embryo transfers in subsequent cycles, whether it be earlier, later, or at the same time.

The primary objective of this clinical trial is to investigate whether vitrified/thawed euploid embryo transfers result in improved pregnancy outcomes when precisely timed using the ora™ test. To achieve this, we propose implementing a randomized clinical trial. The outcomes, including clinical pregnancy rate and live birth rate, will be calculated.

2.2. Test Description

The ora™ test is a Laboratory Developed Test (LDT) performed within a single laboratory. Using NGS, the ora™ test is a miRNA-based endometrial receptivity test designed to identify the optimal window of implantation (WOI) based on miRNAs isolated from plasma processed from peripheral the whole blood samples of the patients.

The results of WOI identification for endometrial receptivity are reported in three statuses: “PRE-RECEPTIVE”, “RECEPTIVE”, and “POST-RECEPTIVE”. The pre-receptivity result, reported as “PRE”, indicates that the endometrium is not yet at peak receptivity at the time of sampling and the WOI is delayed. In the pre-receptivity status, the endometrium is not yet ready for embryo implantation, and it is recommended to delay embryo transfer from the sampling time. The receptive result, which is reported as “WOI”, indicates that the endometrium is at peak receptivity at the time of sampling and is ideal for embryo implantation. Embryo transfer is recommended at the same time of sampling. The post-receptive result, which is reported as “POST”, indicates that the endometrium has past peak receptivity at the time of sampling and the optimal time for embryo implantation has passed. Therefore, embryo transfer is recommended to take place earlier than the sampling time.

Indication For Use

The ora™ test is a Laboratory Developed Test (LDT) designed to analyze the expression profile of miRNAs isolated from plasma. It is intended to identify the optimal window of implantation (WOI) in patients undergoing in vitro fertilization (IVF).

CLINICAL STUDY PROTOCOL

Title: Multi-national, multi-center randomized controlled trial to evaluate the clinical utility of non-invasive endometrial receptivity test (ora™) in patients with implantation failure

Doc. No.	ORA-PTL-2024-01
Version	1.0
Date	2024/01/10

3. Objectives and Endpoints

3.1. Description of the Study

The study is a two-arm, randomized controlled trial that aims to compare clinical pregnancy-related outcomes in different groups. Patients who have experienced at least one failed implantation with a euploid or low-level mosaic (< 30%) embryo transfer in the past two years will be recruited. They will undergo a single frozen embryo transfer, with the timing determined by either ora™ testing or a standardized approach.

3.2. Study Objectives

To evaluate the clinical utility of non-invasive endometrial receptivity test (ora™) in patients with implantation failure.

3.3. Study Endpoints

(a) Primary Endpoint

Clinical pregnancy, defined as presence of one or more intrauterine gestational sacs after 6 weeks estimated gestational age.

(b) Secondary Endpoint

- 1) Ongoing pregnancy, defined as presence of fetal heartbeat after 12 weeks of gestation.
- 2) Live birth, defined as baby survival after 20 weeks of gestation.
- 3) Abortion and miscarriage rates.
- 4) Frequency and intensity of adverse events (AEs).

CLINICAL STUDY PROTOCOL

Title: Multi-national, multi-center randomized controlled trial to evaluate the clinical utility of non-invasive endometrial receptivity test (ora™) in patients with implantation failure

Doc. No.	ORA-PTL-2024-01
Version	1.0
Date	2024/01/10

4. Study Population

4.1. Number of Subjects

The study is expected to enroll up to 800 subjects.

4.2. Inclusion criteria

- (a) Subjects who have at least one implantation failure with a euploid or low-level mosaic (< 30%) embryo transfer in the past two years.
- (b) Females within 28-45 years old.
- (c) Those who agree to undergo one mock cycle for ora™ test and execute single frozen embryo transfer in the later cycle.
- (d) Those who has at least one remaining euploid or low-level mosaic (< 30%) embryo.

4.3. Exclusion Criteria

- (a) Known uterine factor (such as endometriosis, uterine fibroids) impacting the endometrium.
- (b) Presence of any clinically relevant systemic disease (such as immune disease) that contraindicates assisted reproductive technology.
- (c) Body mass index (BMI) exceeds than 30 kg/m².

4.4. Withdrawal criteria

- (a) During the research process of this research project, all subjects can unconditionally choose to withdraw.

	CLINICAL STUDY PROTOCOL	Doc. No.	ORA-PTL-2024-01
	Title: Multi-national, multi-center randomized controlled trial to evaluate the clinical utility of non-invasive endometrial receptivity test (ora™) in patients with implantation failure	Version	1.0
		Date	2024/01/10

5. Study Procedures

5.1. Overall Design

This study aims to enroll up to 800 subjects who have experienced at least one implantation failure with a euploid or low-level mosaic (< 30%) embryo transfer in the past two years. Subjects should have at least one euploid or low-level mosaic (< 30%) embryo for the study. Subjects will be randomly assigned to either the control or study group. In the control group, subjects will simultaneously provide blood samples for the ora™ test and undergo Hormone Replacement Therapy (HRT) frozen embryo transfer during the standard implantation window (day 5 of progesterone supplementation: P+5/120 hours). In the study group, subjects will provide blood samples for the ora™ test during a mock HRT cycle; in the subsequent cycle, the subject will undergo HRT frozen embryo transfer during the period which the implantation window is confirmed as “Receptive” by ora™’s analysis. The study aims to compare pregnancy outcomes to evaluate whether ora™ timing offers clinical advantages to the patients.

Control Group: Euploid embryo transfer at standard implantation window (day 5 of progesterone supplementation: P+5/120 hours)

Study Group: Mock cycle followed by euploid embryo transfer at implantation window confirmed as “Receptive: by ora™’s analysis.

5.2. Subject Recruitment

Subjects with at least one implantation failure with a euploid or low-level mosaic (< 30%) embryo transfer in the past two years will be invited based on the inclusion/exclusion criteria during a private fertility consultation with their physician. Subjects will be recruited for the current study only after presenting their own volition.

5.3. Informed Consent Process and Informed Consent Text

Before each subject is selected into this study, the investigator/researcher is responsible for fully and comprehensively introducing the purpose and possible risks of this study to the subject in written form. Subjects must be informed that they have the right to withdraw from the study at any time and that their personal information will be kept confidential.

A written informed consent form (ICF) must be given to each subject prior to enrollment. It is the investigator's responsibility to obtain informed consent from each subject prior to entry into the study and to keep it in the study file.

5.4. Payment for the Participation

Subjects meeting inclusion/exclusion criteria and do not drop out of the study will be compensated for their participation in the study. The details of compensation will be provided to the subjects in the ICF. The expense for ora™ test will be covered by the Inti, Inc. Taiwan, and the expense of ultrasound, medication and bloodwork to assess the endometrial cycle will be covered by the testing sites. Subjects will be billed in the usual manner for screening, diagnostic costs, IVF/ICSI including egg retrieval and anesthesia, embryo vitrification, and FBT through the hospital or reproductive clinics (the testing sites).

CLINICAL STUDY PROTOCOL

Title: Multi-national, multi-center randomized controlled trial to evaluate the clinical utility of non-invasive endometrial receptivity test (ora™) in patients with implantation failure

Doc. No.	ORA-PTL-2024-01
Version	1.0
Date	2024/01/10

Standard IVF and endometrial preparation medications will be prescribed as per standard clinical practice and covered by the subject or her medical insurance as per usual. Subjects who wish to maintain embryo in cryopreservation will have to pay a standard annual storage fee as per routine.

5.5. Data collection and protection

All data obtained in clinical trials are subject to data protection. The paper informed consent and case report form (CRF) will be stored in a locker on the test facility and/or electronically separately. Investigators/researcher shall not disclose the subject’s name and other identifiable personal data (excluding year of birth/age, weight, height and medical record number (MRN)).

Any documents submitted to Inti Labs do not contain names, but only subject codes. Likewise, data for statistical evaluation can only be accessed under the subject code. Only the researcher can identify the subject's name and other personal information through the code. If the name of a subject needs to be identified for medical reasons during the research, all subjects involved are obliged to keep it confidential.

5.6. Research Process

(a) Randomization:

After signing the ICF, the investigator will assign a **subject code** to each enrolled subject. This subject code will consist of two parts: the center identification number and the subject identification number. For instance, TW01-001.

- 1) The center identification number is structured using the first two letters of the country name followed by a two-digit site number. Examples include TW01, TW02, SG01, JP01, etc.
- 2) Within each age category at each center, subjects will receive a subject identification number assigned based on their order of inclusion in the study. The first subject enrolled will be labeled as 001, followed by 002, and so forth, maintaining chronological order.

Once the subject receives the unique subject code, the subject will be randomized to one of the two study groups through a simple 1: 1 randomization program stratified by center (to avoid bias). The randomization number will be assigned to each subject included in the study, as well as their corresponding group. The randomization program will be set up by the Inti Inc., Taiwan.

For example, the randomization process for a subject attending the initial clinical site in Taiwan:

Subject code	Randomization number	Group
TW01-001	1	Control
TW01-002	2	Study
TW01-003	3	Study
TW01-004	4	Control
TW01-005	5	Control
TW01-006	6	Study

CLINICAL STUDY PROTOCOL

Title: Multi-national, multi-center randomized controlled trial to evaluate the clinical utility of non-invasive endometrial receptivity test (ora™) in patients with implantation failure

Doc. No.	ORA-PTL-2024-01
Version	1.0
Date	2024/01/10

- (b) Subjects will undergo the hormone replacement therapy (HRT) in a frozen embryo transfer (FET) cycle. The HRT treatment cycle will be performed following medical criteria and in accordance with the usual practice of the clinic and the doctors. Ideally, the subjects in the control and study groups should follow identical drug prescription program.
- (c) Endometrial receptivity test by ora™:
- 1) Study group subjects will undergo blood sampling for the ora™ test on the fifth day of progesterone administration in a **mock cycle** (120 ± 3 hours after the first progesterone injection); the control group subjects will undergo blood sampling for the ora™ test and frozen embryo transfer at the standard time (120 ± 3 hours after the first progesterone injection) for data collection.
 - 2) The collected blood samples will be processed into plasma by the researchers, and these samples will then be sent to the Inti Service Laboratory in Taiwan for an endometrial receptivity test. The results, indicating the receptivity timing as determined by ora™, will be provided 10 days later. The results include:
 - a. Receptive Phase: At the time of blood draw, it is the optimal Window of Implantation (WOI) for embryo implantation. It is recommended to perform embryo implantation at the sampling time point.
 - b. Pre-Receptive: At the time of blood draw, it is before the optimal Window of Implantation (WOI). The endometrium is not yet ready for embryo implantation. It is suggested to delay the embryo implantation window by 24 hours.
 - c. Post-Receptive: At the time of blood draw, the endometrium has passed the optimal time for embryo implantation. It is recommended to advance the embryo transfer time by 24 hours.
 - 3) Any subject whose blood sample does not provide adequate information to recommend timing for FET will be withdrawn from the study.

CLINICAL STUDY PROTOCOL

Title: Multi-national, multi-center randomized controlled trial to evaluate the clinical utility of non-invasive endometrial receptivity test (ora™) in patients with implantation failure

Doc. No.	ORA-PTL-2024-01
Version	1.0
Date	2024/01/10

(d) Frozen embryo transfer

On the day of embryo transfer, one of the subject's vitrified, euploid blastocysts will be thawed, and the subject will undergo single embryo transfer. **The frozen embryo transfer in the study group should follow the exact same drug prescriptions and dosage without deviation from the mock cycle.**

- 1) If the subject is assigned to the control group, a single embryo transfer will be performed on the subsequent cycle after randomization. The transfer timing follows the standard HRT protocol at 120 ±3 hours post initiation of progesterone.
- 2) If the subject is assigned to the study group, a single embryo transfer will be performed on the HRT cycle after the mock cycle. The transfer timing is based on the implantation window indicated by ora™ test results.

(e) Results confirmation

- 1) Approximately 10 days following implantation, a serum hCG concentration will be detected.
- 2) Around 6 weeks after estimated gestational age, an ultrasound will be performed to assess the presence of a gestational sac, providing an estimate of clinical pregnancy.
- 3) Around 12 weeks after estimated gestational age, an ultrasound will be performed to assess the presence of a fetal heartbeat, providing an estimate of ongoing pregnancy.
- 4) Around 20 weeks after estimated gestational age, live birth will be evaluated.
- 5) Abortion and miscarriage rates would be calculated.

[figure not shown]

Fig. 1 Flowchart of the clinical trial

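### As worded, the uninformative-sample rule in Section 5.6(c)3 also withdraws control women after their standard-timed transfer and before the primary endpoint

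*Protocol*

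**What the plan says.** Protocol Section 5.6(c) governs ora sampling in both arms. Item 1 describes study-group and control sampling in one sentence, and item 3 then sets the rule: "Any subject whose blood sample does not provide adequate information to recommend timing for FET will be withdrawn from the study". It makes no distinction by arm.

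For controls, Section 5.1 states: "In the control group, subjects will simultaneously provide blood samples for the ora™ test and undergo Hormone Replacement Therapy (HRT) frozen embryo transfer". Section 5.6(c)1 agrees: "the control group subjects will undergo blood sampling for the ora™ test and frozen embryo transfer at the standard time", and gives the time and purpose of the sample as "120 ± 3 hours after the first progesterone injection) for data collection". Section 5.6(d)1 fixes control timing without reference to the test: "The transfer timing follows the standard HRT protocol at 120 ±3 hours post initiation of progesterone".

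On turnaround, Section 5.6(c)2 says: "The results, indicating the receptivity timing as determined by ora™, will be provided 10 days later". On the pregnancy test, Section 5.6(e)1 says: "Approximately 10 days following implantation, a serum hCG concentration will be detected". The primary endpoint (Sections 3.3 and 5.6(e)2) is a gestational sac on ultrasound at around 6 weeks of gestation.

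Study-group women are sampled in a mock cycle, one cycle before transfer. Section 4.4, on withdrawal, says only that "all subjects can unconditionally choose to withdraw". The synopsis states that the trial is not blinded.

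**The concern.** A control woman is transferred exactly as her arm requires, and her sample has no role in that. If the sample proves uninformative, the rule read literally still takes her out of the study. Her outcome would have been valid under the arm definition, and the scheduled ultrasounds would have recorded it. Instead her follow-up stops before the primary endpoint is assessed, and with it the collection of ongoing pregnancy, live birth, miscarriage and adverse event data.

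This differs from the question of women who never reach transfer. These women did reach it, so they belong in the per-transfer comparison of Section 7.2. The rule is also a post-randomisation exclusion that falls at different points in the two arms: before transfer in the study group, after transfer in the controls. Among controls it may take effect when a pregnancy test has already been read, and the protocol contains no safeguard against the rule being applied unevenly. A statistical analysis plan can define analysis sets, but it cannot recover outcomes that were never collected.

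**Working it through.** **1. Order of events, from Sections 5.1 and 5.6**

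| Event | Control | Study group |
|---|---|---|
| ora sample | day 0, at transfer | mock cycle, before any transfer |
| Transfer | day 0, at 120 ± 3 h of progesterone | later cycle, timed by ora |
| ora result, and so item 3 withdrawal | about day 10, after transfer | about 10 days after the mock-cycle sample, before transfer |
| Serum hCG | about day 10 | about 10 days after the later transfer |
| Primary endpoint | about 6 weeks of gestation | about 6 weeks of gestation |

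The start of the 10-day turnaround is not defined. If it runs from laboratory receipt, the control result comes later still. On either reading it follows transfer.

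**2. The plan's own figures (Section 7.1)**

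Inputs: 50% against 60%, alpha 0.05, power 0.80, 325 per group, 800 enrolled. The usual formula is n = [z_α√(2p̄q̄) + z_β√(p₁q₁ + p₂q₂)]² / d², with p̄ = 0.55 and d = 0.10.

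- Two-sided: [1.960 × 0.7036 + 0.8416 × 0.7]² / 0.01 gives 388 per group.
- One-sided: [1.645 × 0.7036 + 0.8416 × 0.7]² / 0.01 gives 305. With continuity correction it gives 325, the stated figure.
- Enrolment: 650 / (1 − 0.1875) = 800, so 800 allows for 18.75% loss.

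The sidedness of alpha is a separate matter. It is noted only because the power figures in step 5 are two-sided.

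**3. Controls removed**

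The protocol gives no inadequate-sample rate f, so I assume 2%, 5% and 10%. With 1:1 allocation of 800 there are 400 controls, and k = 400f gives 8, 20 and 40. This takes all 400 to reach transfer. With 10-20% lost earlier, 320-360 are transferred and the range is 0.02 × 320 = 6.4 to 0.10 × 360 = 36.

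**4. Effect on the observed control rate**

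Assume a true rate of 50%, that is 200 of 400. The extreme bounds are 200/(400 − k) if every removed woman was not pregnant, and (200 − k)/(400 − k) if every one was.

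| f | k | All removed pregnant | All removed not pregnant |
|---|---|---|---|
| 2% | 8 | 192/392 = 49.0% | 200/392 = 51.0% |
| 5% | 20 | 180/380 = 47.4% | 200/380 = 52.6% |
| 10% | 40 | 160/360 = 44.4% | 200/360 = 55.6% |

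A milder case: adequacy is unrelated to outcome, but the rule is enforced only for women with one hCG result (hCG being taken as a stand-in for clinical pregnancy). Half of k is then removed. At 5%, the rate is 200/390 = 51.3% if only negatives are removed and 190/390 = 48.7% if only positives are. At 10%, it is 200/380 = 52.6% and 180/380 = 47.4%.

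If adequacy and enforcement are both unrelated to outcome, the expected rate stays at 50%.

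**5. Power**

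Two-sided 0.05, 50% against 60%, 10% other dropout (360 per arm before the rule). With equal arms, power = Φ([d√n − 1.960√(2p̄q̄)] / √(p₁q₁ + p₂q₂)). For example, n = 342 gives Φ([1.849 − 1.379] / 0.7) = 74.9%. The right-hand column uses the same test with unequal arms.

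| f | Rule in both arms | Rule in study arm only |
|---|---|---|
| 2% | 76.2% | 76.6% |
| 5% | 74.9% | 76.0% |
| 10% | 72.6% | 74.8% |

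Extending the rule to controls costs about 0.4, 1.1 and 2.2 points.

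**The case against.** **Scope.** The rule concerns samples too poor to support a timing recommendation, and only study-group samples serve that purpose. It may have been meant for the study group alone. The flowchart (Fig. 1) is not reproduced in the text at hand, so it cannot be checked for an arm-specific exit. This stands as a reading of intent. But the wording covers every subject, in a subsection dealing with both arms, and no exemption appears in the text. If the narrow reading was intended, a few words settle it.

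**Like with like.** Applying one rule to both arms could be defended as keeping them comparable. That has some force, and it is why the control half should not be repaired alone: an exclusion left only in the study group would still be post-randomisation. It does not justify removing controls, because the failure is observed in different cycles and on opposite sides of the transfer.

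**What a reader might infer too readily:**

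- *That control data already collected are deleted.* The protocol says the woman is withdrawn, not that her existing data are discarded. Handling of withdrawn subjects may lie in an analysis plan that is not at hand. What follows from the text is the end of further follow-up.
- *That the primary outcome is known when she is withdrawn.* At about day 10 only hCG may be known; the primary endpoint is assessed at about 6 weeks.
- *That the sponsor's laboratory judges adequacy knowing the outcome.* Section 5.5 has documents sent under subject code only. The sponsor reviews case report forms (Section 7.3), but nothing shows that the laboratory sees hCG. There is a missing safeguard, not evidence of selection.
- *That Section 4.4 contradicts the rule.* It grants a right to withdraw and does not say that this is the only route.

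**Size.** The failure rate is assumed, the widest bounds need every removed woman to share one outcome, and Section 7.1 already budgets for 10-20% dropout. All of this stands.

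**Conclusion.** The point holds as a defect of wording with real consequences for data. Followed as written, Section 5.6(c)3 ends follow-up of controls who were validly transferred, because of a test that played no part in their timing, and does so before the primary endpoint. It acts at a different point in each arm.

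The likely size is modest: 8-40 women at an assumed 2-10% of 400 controls, with no bias and a power cost of about 0.4-2.2 points if adequacy is unrelated to outcome. The bounds in step 4 show how far selective loss could move the control rate against a 10-point target difference; they do not predict that it will. The case rests on an avoidable loss that analysis cannot repair and on an open route to uneven exclusion, not on a demonstrated large bias. It should be fixed, but it does not by itself undermine the trial.

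**What to change.** - In Section 5.6(c)3, state that an uninformative sample does not withdraw a control subject. Record her ora result as missing, and keep her in pregnancy, miscarriage and adverse event follow-up and in the primary analysis.
- For study-group subjects, separate having no ora timing available from leaving the study, so that any outcomes are still collected. This concerns data retention only; how such women are managed clinically is for the investigators and the sponsor to specify.
- Make both changes together, so that the repair does not leave an exclusion in one arm only.
- Cross-refer Section 4.4 to the revised rule.

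The cost is a protocol wording change with the usual ethics committee approval (Section 9.1). For controls it needs no new visits or samples, since the ultrasounds are already scheduled. A few women will have a missing ora result in exploratory tables.

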5.7. Schedule of Activities

This project is expected to be implemented for 6-15 months for individual sites depending on the allocated subject size.

CLINICAL STUDY PROTOCOL

Title: Multi-national, multi-center randomized controlled trial to evaluate the clinical utility of non-invasive endometrial receptivity test (ora™) in patients with implantation failure

Doc. No.	ORA-PTL-2024-01
Version	1.0
Date	2024/01/10

6. Risk and benefit analysis

The execution process of this study follows the standard procedures of in vitro fertilization (IVF), except for the blood specimen collection for endometrial receptivity testing. Rigorous standard operating procedures have been established for the specimen collection process, specimen storage, and specimen transportation. Only relatively sensitive subjects may experience discomfort during blood specimen collection, but noticeable improvement is observed after a period of rest.

7. Statistical considerations

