7.1. Sample size calculation

The sample size calculation for the two-armed endpoint suggests that obtaining data from 650 participants (325 subjects for each group). This sample size is adequate to detect a 10% difference in clinical pregnancy outcomes between groups given an alpha level of $p < 0.05$ and a power of 0.8 and using 50% anticipated LB in the control arm (based on current success rates among euploid embryo transfers conducted with standard timing protocol). Accounting for 10-20% dropout rate, the goal is to enroll 800 subjects in total.

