7.2. Data Evaluation and Statistical Considerations

- (a) The outcome of clinical pregnancy and live birth rate, etc. per transfer will be compared between the study and control groups by chi-square analysis.
- (b) The quantitative outcomes such as gestational age and BMI, etc. will be compared between treatment groups by the Mann-Whitney U test.

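### Live birth is evaluated at about 20 weeks of gestation, with no outcome check at delivery, so the endpoint as written is ongoing pregnancy at 20 weeks

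*Protocol*

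**What the plan says.** The synopsis and section 3.3 of the protocol give the same definition of this secondary endpoint: "Live birth, defined as baby survival after 20 weeks of gestation". Neither mentions delivery.

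Section 5.6(e) lists the outcome checks: serum hCG about 10 days after transfer, ultrasound at about 6 weeks for a gestational sac, and ultrasound at about 12 weeks for a heartbeat. The last dated item is "Around 20 weeks after estimated gestational age, live birth will be evaluated", for which no method is named. The item after it says only that abortion and miscarriage rates will be worked out.

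Section 5.7 contains no visit schedule, only a duration: "This project is expected to be implemented for 6-15 months for individual sites depending on the allocated subject size". The synopsis has "Study Period: 6-15 months".

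Live birth is used as an outcome in three places:

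- Section 2.1: "The outcomes, including clinical pregnancy rate and live birth rate, will be calculated".
- Synopsis, statistical methodology: "The outcome of clinical pregnancy, ongoing pregnancy and live birth rate per transfer will be compared", by chi-square.
- Section 7.2: "The outcome of clinical pregnancy and live birth rate, etc", again per transfer and by chi-square.

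**The concern.** A live birth is known only once there has been a delivery. Here the endpoint is assessed about halfway through pregnancy, and nothing later is scheduled. The trial would then report a between-arm comparison called live birth without having ascertained any births.

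The objective is the clinical utility of the test, and readers will give weight to a live-birth result. There is also a practical risk: some sites may close follow-up at 20 weeks while others go on to record deliveries, so that one variable carries two meanings across a multi-national trial.

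**Working it through.** **Two readings of the definition, set against the assessment time**

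| Reading of survival after 20 weeks | What a check at about 20 weeks can record | Result |
|---|---|---|
| The pregnancy is alive at the 20-week check | Pregnancy still ongoing at 20 weeks | Measurable, but it is not live birth; the label is wrong |
| A baby is born alive, counted if gestation has passed 20 weeks | Nothing yet, since continuing pregnancies are undelivered | Not measurable at that time |

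Neither reading gives a live-birth rate from the schedule as written.

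**Timing**

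Assumptions, not in the protocol: blastocyst transfer at 2 weeks 5 days of gestation (day 19), term delivery at 37-40 weeks, 30.44 days per month.

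- 20 weeks: 140 − 19 = 121 days after transfer; 121 / 30.44 = 4.0 months.
- 37 weeks: 259 − 19 = 240 days; 240 / 30.44 = 7.9 months.
- 40 weeks: 280 − 19 = 261 days; 261 / 30.44 = 8.6 months.
- From the 20-week check to term: 17-20 weeks, or 119-140 days; 119 / 30.44 = 3.9 and 140 / 30.44 = 4.6 months.

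As supporting evidence only: if the 6-15 month period includes follow-up, which the protocol does not say, a 6-month site could not observe a term birth in either arm, because 7.9 is greater than 6. The finding does not depend on this.

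**Size of the miscount**

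The protocol calculates nothing specific to this endpoint, so there is no figure of its own to reproduce. Inputs from section 7.1: 325 women per group, a 50% control rate and a 10% difference, read as absolute (60% in the study arm). Assumption, not from the protocol: 0.5-2% of pregnancies are lost between 20 weeks and birth.

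Women miscounted = pregnancies × loss rate.

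- Control: 0.50 × 325 = 162.5 pregnancies. × 0.005 = 0.8; × 0.02 = 3.3. As a share of 325: 0.25 to 1.0 percentage points.
- Study: 0.60 × 325 = 195 pregnancies. × 0.005 = 1.0; × 0.02 = 3.9. As a share of 325: 0.3 to 1.2 percentage points.

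**Effect on the comparison**

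If the loss rate is equal in both arms, the difference changes by 10 points × 0.005 = 0.05 to 10 points × 0.02 = 0.2 percentage points.

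**The case against.** **The protocol is consistent with itself.** Each pregnancy endpoint is defined as after a given week and checked around that week: 6 and 6, 12 and 12, 20 and 20. On that pattern the definition and the timing agree, and only the name is wrong. This is a fair account of the first reading. It confirms that what is collected is 20-week ongoing pregnancy, and the analysis would still report that as live birth.

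**Delivery data may be collected anyway.** Gestational age is listed as a quantitative outcome in the synopsis and section 7.2, which may mean age at delivery. Section 8.2 counts fetal death and birth defects as serious adverse events. The flowchart in Fig. 1 could not be read and might show a delivery follow-up. These points limit how firmly one can say that nothing happens after 20 weeks. However, gestational age is not explained, and safety reporting is event-driven and does not give every pregnancy an endpoint value. A delivery box in the figure would contradict section 5.6(e) and would need reconciling with it.

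**The base for the miscount is uncertain.** Section 7.1 powers a difference in clinical pregnancy but takes its control rate from "using 50% anticipated LB in the control arm". If the 50% is a clinical pregnancy rate at 6 weeks, fewer pregnancies remain at 20 weeks and the miscount is overstated. If it is a true live-birth rate, the 20-week count is slightly higher. At 2% loss, 162.5 / 0.98 = 165.8, so 3.3 women are miscounted in the control arm; 195 / 0.98 = 199.0, so 4.0 in the study arm. The order of magnitude stands either way.

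**The effect on the comparison is negligible.** Under equal loss this is right, and it is conceded. The fault lies in what the endpoint measures; no bias between arms is claimed.

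**Conclusion.** The concern holds and should be fixed. The wording conflict rests on the protocol text alone. That no outcome check at delivery is scheduled rests on the readable text, without Fig. 1. The timing figures rest on the assumed gestational age at transfer and term range, and the miscount on the assumed 0.5-2% late loss. The consequence is for the conclusion the trial may draw: the data as scheduled do not support a statement about live birth. A statistical analysis plan could not repair this, because it cannot recover delivery outcomes that were never collected.

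**What to change.** Choose one of two changes.

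**(a) Measure live birth.** Define it as delivery of at least one live-born baby at or after 20 completed weeks, keeping the protocol's own threshold. Ascertain it after delivery by record check or phone contact. Count follow-up from each woman's own transfer, and state that the 6-15 month period allows for it. The cost is one contact or record check per ongoing pregnancy, and final data for this endpoint about 3.9-4.6 months after the 20-week check for term deliveries. The primary endpoint is not delayed. This has to be in place before sites close follow-up.

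**(b) Stop at 20 weeks and say so.** Rename the endpoint *ongoing pregnancy at 20 weeks* in the synopsis and sections 2.1, 3.3, 5.6(e) and 7.2, and make no live-birth claim. The change is wording only, but it gives up any conclusion on live birth.

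Under either option, check that Fig. 1 agrees with section 5.6(e).
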